6.4.3 Exploratory Efficacy Endpoints

Exploratory efficacy endpoints will be analyzed using the same methods as described for the secondary endpoints in Section [6.4.2](#), where appropriate.

6.5 SAFETY ANALYSES

Safety analyses will be conducted on all patients who received at least one dose of study drug, with patients grouped according to the treatment received.

Safety will be assessed through summaries of exposure to study treatment, adverse events, laboratory test results, vital signs, and ECGs.

All verbatim adverse event terms will be mapped to MedDRA thesaurus terms, and adverse event severity will be graded according to NCI CTCAE v5.0 scale. All adverse events, serious adverse events, adverse events leading to death, adverse events of special interest, adverse events leading to discontinuation from study treatment, adverse events leading to discontinuation from study, and treatment-emergent adverse events will be summarized by treatment groups. A treatment-emergent adverse event is defined as any new adverse event reported or worsening of an existing condition on or after the first dose of study drug during. Deaths and cause of death will be summarized.

Relevant laboratory, vital sign, and ECGs will be summarized by appropriate descriptive statistics by treatment groups.

6.6 PHARMACOKINETIC ANALYSES

The PK analysis population will consist of patients who received at least one dose of MSTT1041A or UTTR1147A and have sufficient data to enable estimation of key parameters (e.g., C_{max}), with patients grouped according to treatment received.

Estimates for the PK parameters will be tabulated and summarized (mean, standard deviation, coefficient of variation, median, minimum, and maximum), as appropriate. Individual and mean serum MSTT1041A or UTTR1147A concentration versus time data will be tabulated by dose level. Additional PK analyses will be conducted as appropriate.

6.7 IMMUNOGENICITY ANALYSES

The immunogenicity analysis population will consist of all patients with at least one ADA assessment. Patients will be grouped according to treatment received, or, if no treatment is received prior to study discontinuation, according to treatment assigned.

The numbers and proportions of ADA-positive subjects and ADA-negative subjects at baseline (baseline prevalence) and after drug administration (postbaseline incidence) will be summarized by treatment group. When determining postbaseline incidence, subjects are considered to be ADA positive if they are ADA negative or have missing data at baseline but develop an ADA response following study drug exposure (treatment-induced ADA response), or if they are ADA positive at baseline and the titer of one or more postbaseline samples is at least 0.60 titer unit greater than the titer of the baseline sample (treatment-enhanced ADA response). Subjects are considered to be ADA negative if they are ADA negative or have missing data at baseline and all postbaseline samples are negative, or if they are ADA positive at baseline but do not have any postbaseline samples with a titer that is at least 0.60 titer unit greater than the titer of the baseline sample (treatment unaffected).

The relationship between ADA status and safety, efficacy, PK, and biomarker endpoints may be analyzed and reported via descriptive statistics.

6.8 BIOMARKER ANALYSES

No formal statistical analysis of exploratory biomarkers will be performed. Data may be analyzed in the context of this study and in aggregate with data from other studies.

6.9 OPTIONAL INTERIM ANALYSES

Other than the cumulative data review by the DMC for benefit/risk assessment, no formal efficacy interim analyses are planned at this time. The DMC, after reviewing unblinded data, may recommend that a formal efficacy interim analysis be performed. Furthermore, to adapt to information that may emerge during the course of this study, the Sponsor may choose to add a formal interim analysis at the recommendation of the DMC.

The interim analysis will be conducted by DMC. The decision to conduct the optional interim analysis, along with the rationale, timing, and statistical details for the analysis, will be documented in the Sponsor's trial master file prior to the conduct of the interim analysis. The DMC Charter will be updated to document potential recommendations the DMC can make as a result of the analysis (e.g., stop the study for positive efficacy, stop the study for futility).

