3.1.2 Data Monitoring Committee

A DMC will review unblinded safety and efficacy data to assess whether treatment with MSTT1041A or UTTR1147A is associated with toxicity or worsening disease. Members of the DMC will include representatives from Clinical Science and Drug Safety who are not directly involved in the study and representatives from Biostatistics and Statistical Programming and Analysis and may invite representatives from other functional areas on an ad-hoc basis when additional expertise is required (e.g., Clinical Pharmacology, Research). The DMC will also include at least two external experts in the field, and additional experts may be added during the course of the study.

The DMC will review cumulative safety data through at least Day 14 after the first 30 patients have been enrolled or after the first 30 days from the first patient enrolled (whichever occurs first). Subsequently, the DMC will review cumulative safety and efficacy data after each additional 75 patients have been enrolled or 3 months (whichever occurs first); for example, once *approximately* 75, 150, 225, and 300 patients have enrolled. Ad hoc meetings may be held at the request of the DMC or Sponsor at any time to address potential safety concerns. The DMC will have access to all available data at each review to perform an overall benefit/risk assessment. Data to be reviewed will include demographics, concomitant medications, study drug administration, ECGs, laboratory data, adverse events, serious adverse events, adverse events of special interest, and deaths.

MSTT1041A/UTTR1147A—Genentech, Inc.
36/Protocol GA42469, Version 4

At the time of each review, the DMC can make one of the following recommendations: the trial continues as planned, additional analyses need to be performed, enrollment is held pending further safety evaluations or other study modifications, the MSTT1041A or UTTR1147A arm of the trial is stopped, or the trial is stopped. Final decisions will rest with the Sponsor's study team.

Any outcomes of these reviews that affect study conduct will be communicated in a timely manner to the investigators for notification of their respective Institutional Review Board (IRB) or Ethics Committee (EC).

A detailed description of the procedures, data flow, and meeting schedule will be provided in the DMC Charter.

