6.1 DETERMINATION OF SAMPLE SIZE

A total of approximately 390 patients will be randomly allocated in a 2:2:1:1 ratio to receive MSTT1041A, UTTR1147A, or their matching placebos. The sample size provides approximately 80% power using a log-rank Chi-square test to detect a 7-day difference between treatment groups in time to *recovery*, *defined as time to score of 1 or 2 on the 7-category ordinal scale (whichever occurs first)*, under the following assumptions: median time to improvement in the placebo group is 21 days, with 28 days follow-up, and using a one-sided 5% alpha. The minimal detectable difference is expected to be approximately 5.3 days.

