6.4 EFFICACY ANALYSES

Efficacy analyses will be conducted on the mITT population, consisting of all patients randomized in the study who received at least one dose of study drug, with patients grouped according to the treatment assigned at randomization.

MSTT1041A/UTTR1147A—Genentech, Inc.
81/Protocol GA42469, Version 4

MSTT1041A placebo and UTTR1147A placebo will be pooled in efficacy analyses. Comparison of efficacy will be performed between each of the two treatment groups and the pooled placebo. That is, there are two comparisons:

- MSTT1041A with pooled placebo
- UTTR1147A with pooled placebo

Sensitivity analyses to evaluate the robustness of results will be conducted with comparison of primary efficacy endpoint between MSTT1041A and MSTT1041A placebo, and between UTTR1147A and UTTR1147A placebo.

Details on analysis methods, sensitivity analyses, hypothesis testing, and type I error control across treatment groups will be specified in the Data Analysis Plan (DAP).

Unless otherwise noted, analyses of efficacy outcome measures will be adjusted by stratification factors (the need for invasive mechanical ventilation [yes vs. no] and region).

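### Section 6.9 lets an efficacy interim be added after unblinded efficacy review, with its statistical rule set only then, so the one-sided 5% level is not guaranteed

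*Protocol*

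**What the plan says.** Protocol Section 3.1.2 gives the DMC unblinded safety and efficacy data. After a first safety review, "Subsequently, the DMC will review cumulative safety and efficacy data after each additional 75 patients have been enrolled or 3 months", with about 75, 150, 225 and 300 enrolled patients as the example.

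Section 6.9 states that no formal efficacy interim is planned, and then opens one: "The DMC, after reviewing unblinded data, may recommend that a formal efficacy interim analysis be performed". The Sponsor may add the interim on that recommendation, and the DMC conducts it. The decision, its rationale, the timing and the statistical details are to be recorded in the Sponsor's "trial master file prior to the conduct of the interim analysis". The DMC Charter is updated with the possible recommendations, which include stopping for efficacy or for futility.

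Section 6.1 sets the design level, "using a one-sided 5% alpha". No section gives a spending function, a boundary, a maximum number of looks or an adjusted final level. Section 6.4 leaves type I error control across treatment groups to the Data Analysis Plan, and Section 6.4.2 does so for secondary endpoints. Neither mentions repeated looks. A methods paper on alpha spending is in the reference list, but Section 6.9 neither cites nor adopts it.

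**The concern.** The order of events is the difficulty. The DMC first sees cumulative unblinded efficacy results. An interim may then be recommended because of them, and only after that must its timing and rule be fixed. The interim data include the data that prompted it. A rule filed before the interim but after the unblinded review is not pre-specified in the sense that protects the error rate.

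This is not a matter left to the Data Analysis Plan. Section 6.9 itself names the place (the trial master file) and the time (before the interim is run). If the trial stopped early for efficacy, the claim could be challenged because its boundary was chosen when the result was already visible to those who asked for the analysis.

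**Working it through.** **1. The plan's own power figure.** Section 6.1: "A total of approximately 390 patients will be randomly allocated in a 2:2:1:1 ratio", and Section 6.4: "MSTT1041A placebo and UTTR1147A placebo will be pooled in efficacy analyses". Each comparison is therefore 130 against 130. Section 6.1 also gives "The sample size provides approximately 80% power using a log-rank Chi-square test to detect a 7-day difference between treatment groups" and "median time to improvement in the placebo group is 21 days, with 28 days follow-up".

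- With exponential times (an assumption), medians of 14 and 21 days give a recovery rate ratio of 21/14 = 1.5.
- Recovered by Day 28: 1 − 2^(−28/14) = 0.750 and 1 − 2^(−28/21) = 0.603. Expected events: 130 × (0.750 + 0.603) = 175.9.
- Schoenfeld: ln(1.5) × √(175.9/4) = 2.689; power = Φ(2.689 − 1.645) = 85.2%. A log-rank simulation gives 85.0%.

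The stated figure of about 80% is reached only with an unstated event loss of about 10% to 15% (81.8% to 79.8%). This does not affect the present point; 85.2% serves below as the power with no interim.

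**2. Model for the looks.** Reviews at 75, 150, 225 and 300 patients and a final analysis at 390 give information fractions of 0.192, 0.385, 0.577, 0.769 and 1. Information is assumed proportional to enrolment. Under the null, the Z statistics at fractions s < t have correlation √(s/t). The final critical value with no interim is 1.645.

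**3. Spending functions (one-sided α = 0.05).**

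- O'Brien-Fleming-type: 2[1 − Φ(1.96/√t)]. At 225 patients, 1.96/√0.577 = 2.58, so 0.0099 is spent; the interim bound is z = 2.331 and the final bound 1.675 (p = 0.047).
- Pocock-type: 0.05 × ln[1 + (e − 1)t]. At 225 patients 0.0344 is spent; the bounds are 1.819 and 1.907.

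**4. Type I error per comparison.** The fixed-review row is bivariate normal: 1 − P(Z₁ ≤ 1.645, Z₂ ≤ 1.645). The other rows are from null simulation, 2,000,000 paths for all but the last. The trigger thresholds (Z above 1.0, 1.28 or 1.645 at a DMC review) are assumptions. In the two trigger rows with spending boundaries, the interim falls either at the triggering review or at the next one.

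| Rule | Type I error |
|---|---|
| No interim | 5.0% |
| One interim at a fixed review, nominal 5%, final unadjusted | 9.0%, 8.4%, 7.8%, 7.0% at 75, 150, 225, 300 |
| One interim at the review after the trigger, nominal 5%, final unadjusted | 8.6%, 8.3%, 7.4% for the three triggers |
| O'Brien-Fleming-type boundary chosen after the trigger, final adjusted | 4.9% to 5.2% |
| Pocock-type boundary chosen after the trigger, final adjusted | 5.3% to 7.6% |
| Interim called only if the boundary is already crossed, otherwise full 5% final: O'Brien-Fleming-type | 5.8% |
| The same: Pocock-type | 9.0% |
| Fixed one-sided 0.0005 at all four reviews, full 5% final | 5.0% |

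**5. Cost of a rule fixed in advance (O'Brien-Fleming-type, α held at 5.0%).** One look at 225 gives power 84.8%. All four reviews as looks (bounds 4.34, 2.96, 2.35, 2.01, final 1.73) give 84.2%. Against 85.2%, the losses are 0.4 and 1.0 points.

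**The case against.** The strongest reply is that the boundary matters more than when it was written. With an O'Brien-Fleming-type boundary chosen after the DMC has seen Z above 1, the error is still about 5.0%, and a conditional-error method could also hold 5% after an unplanned look. That stands. A reader might infer that a rule written after unblinding can never restore the level; the calculations contradict this. What remains is that Section 6.9 commits to no such rule.

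A reader might also infer an error of 13.1% per comparison, or a 21.7% chance that at least one drug is declared effective. Those figures come from claiming efficacy at nominal 5% at all four routine reviews and at the end. The protocol does not provide for that. Section 6.9 separates the benefit/risk reviews from an optional interim, the routine recommendations in Section 3.1.2 name no stop for efficacy, and no section proposes an unadjusted test. One unadjusted interim run on the very data that triggered it would give 10.4% to 13.1%, which is likewise a worst case. Of the 21.7%, 8.8% is present with no interim at all, because two drugs are tested against a shared placebo (correlation 0.5). Control of that part is left to the Data Analysis Plan.

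Three further replies carry some weight. The DMC only recommends and the Sponsor decides. Section 4.2.2 keeps the Sponsor blinded apart from prespecified personnel such as DMC members. Section 3.1.2 names no recovery statistic in its list of data to be reviewed. However, Section 3.1.2 does give the DMC unblinded efficacy data and all available data, seats Sponsor-function representatives on it, and Section 6.9 does not say who writes the statistical details.

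**Conclusion.** The point holds in a limited form: the one-sided 5% level is not guaranteed, which is weaker than saying it is lost. Depending on the rule chosen after unblinded review, the error per comparison is about 5% to 6% (O'Brien-Fleming-type), about 5% to 9% (Pocock-type), or about 7% to 9% (one unadjusted interim, at a fixed review or the review after a trigger). These ranges rest on information proportional to enrolment and on assumed trigger thresholds, and they leave aside multiplicity across the two drugs. The Data Analysis Plan and the Charter are not at hand and may add a rule. Even so, the protocol itself permits the details to be set after the data are seen. This is a cheap improvement to the plan and does not invalidate the planned final analysis.

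**What to change.** Before the first unblinded efficacy review, state in Section 6.9 and the DMC Charter that:

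- any added efficacy interim uses a named O'Brien-Fleming-type alpha-spending function on recovery events, with the final level adjusted accordingly, or else a one-sided 0.0005 Haybittle-Peto boundary;
- no stop for positive efficacy is allowed outside that rule;
- the rule is written by personnel without access to unblinded data.

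If only an interim that is actually called spends alpha, a small excess can remain (up to 5.8% in the adverse case above). Counting each unblinded efficacy review as a look removes it.

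The cost is one paragraph in each document. An early efficacy stop would need strong evidence, and power falls by about 1 point or less (85.2% to between 84.8% and 84.2% with spending). The DMC's safety and benefit/risk role is unchanged.

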7. DATA COLLECTION AND MANAGEMENT

7.1 DATA QUALITY ASSURANCE

The Sponsor will be responsible for data management of this study, including quality checking of the data. Data entered manually will be collected via EDC through use of eCRFs. Sites will be responsible for data entry into the EDC system. In the event of discrepant data, the Sponsor will request data clarification from the sites, which the sites will resolve electronically in the EDC system.

The Sponsor will produce an EDC Study Specification document that describes the quality checking to be performed on the data. Central laboratory data will be sent directly to the Sponsor, using the Sponsor's standard procedures to handle and process the electronic transfer of these data.

eCRFs and correction documentation will be maintained in the EDC system's audit trail. System backups for data stored by the Sponsor and records retention for the study data will be consistent with the Sponsor's standard procedures.

7.2 ELECTRONIC CASE REPORT FORMS

eCRFs are to be completed through use of a Sponsor-designated EDC system. Sites will receive training and have access to a manual for appropriate eCRF completion. eCRFs will be submitted electronically to the Sponsor and should be handled in accordance with instructions from the Sponsor.

All eCRFs should be completed by designated, trained site staff. eCRFs should be reviewed and electronically signed and dated by the investigator or a designee.

At the end of the study, the investigator will receive patient data for his or her site in a readable format that must be kept with the study records. Acknowledgement of receipt of the data is required.

7.3 SOURCE DATA DOCUMENTATION

Due to the pandemic situation and resulting restrictions to hospital access, data monitoring may be performed remotely or on-site. Study monitors will perform ongoing data review to confirm that critical protocol data (i.e., source data) entered into the eCRFs by authorized site personnel are accurate and complete. Sites will be asked to implement a QC step of a second person reviewing the data entry in the eCRF where possible.

Source documents (paper or electronic) are those in which patient data are recorded and documented for the first time. They include, but are not limited to, hospital records, clinical and office charts, laboratory notes, memoranda, patient-reported outcomes (PROs), evaluation checklists, pharmacy dispensing records, recorded data from automated instruments, copies of transcriptions that are certified after verification as being accurate and complete, microfiche, photographic negatives, microfilm or magnetic media, X-rays, patient files, and records kept at pharmacies, laboratories, and medico-technical departments involved in a clinical trial.

Before study initiation, the types of source documents that are to be generated will be clearly defined in the Trial Monitoring Plan. This includes any protocol data to be entered directly into the eCRFs (i.e., no prior written or electronic record of the data) and considered source data.

Source documents that are required to verify the validity and completeness of data entered into the eCRFs must not be obliterated or destroyed and must be retained per the policy for retention of records described in Section [7.5](#).

To facilitate source data verification and review, the investigators and institutions must provide the Sponsor direct access to applicable source documents and reports for trial-related monitoring, Sponsor audits, and IRB/EC review. The study site must also allow inspection by applicable health authorities.

MSTT1041A/UTTR1147A—Genentech, Inc.
86/Protocol GA42469, Version 4

7.4 USE OF COMPUTERIZED SYSTEMS

When clinical observations are entered directly into a study site's computerized medical record system (i.e., in lieu of original hardcopy records), the electronic record can serve as the source document if the system has been validated in accordance with health authority requirements pertaining to computerized systems used in clinical research. An acceptable computerized data collection system allows preservation of the original entry of data. If original data are modified, the system should maintain a viewable audit trail that shows the original data as well as the reason for the change, name of the person making the change, and date of the change.

7.5 RETENTION OF RECORDS

Records and documents pertaining to the conduct of this study and the distribution of IMP, including eCRFs, data (if applicable), Informed Consent Forms, laboratory test results, and medication inventory records, must be retained by the Principal Investigator for 15 years after completion or discontinuation of the study or for the length of time required by relevant national or local health authorities, whichever is longer. After that period of time, the documents may be destroyed, subject to local regulations.

No records may be disposed of without the written approval of the Sponsor. Written notification should be provided to the Sponsor prior to transferring any records to another party or moving them to another location.

Roche will retain study data for 25 years after the final study results have been reported or for the length of time required by relevant national or local health authorities, whichever is longer.

8. ETHICAL CONSIDERATIONS

8.1 COMPLIANCE WITH LAWS AND REGULATIONS

This study will be conducted in full conformance with the ICH E6 guideline for Good Clinical Practice and the principles of the Declaration of Helsinki, or the applicable laws and regulations of the country in which the research is conducted, whichever affords the greater protection to the individual. The study will comply with the requirements of the ICH E2A guideline (Clinical Safety Data Management: Definitions and Standards for Expedited Reporting). Studies conducted in the United States or under a U.S. Investigational New Drug (IND) Application will comply with U.S. FDA regulations and applicable local, state, and federal laws. Studies conducted in the European Union or European Economic Area will comply with the E.U. Clinical Trial Directive (2001/20/EC) and applicable local, regional, and national laws.

8.2 INFORMED CONSENT

The Sponsor's sample Informed Consent Form (and ancillary sample Informed Consent Forms such as an Assent Form or Mobile Nursing Informed Consent Form, if applicable) will be provided to each site. If applicable, it will be provided in a certified translation of

MSTT1041A/UTTR1147A—Genentech, Inc.

87/Protocol GA42469, Version 4

the local language. The Sponsor or its designee must review and approve any proposed deviations from the Sponsor's sample Informed Consent Forms or any alternate consent forms proposed by the site (collectively, the "Consent Forms") before IRB/EC submission. The final IRB/EC-approved Consent Forms must be provided to the Sponsor for health authority submission purposes according to local requirements.

If applicable, the Informed Consent Form will contain separate sections for any optional procedures. The investigator or authorized designee will explain to each patient the objectives, methods, and potential risks associated with each optional procedure. Patients will be told that they are free to refuse to participate and may withdraw their consent at any time for any reason. A separate, specific signature will be required to document a patient's agreement to participate in optional procedures. Patients who decline to participate will not provide a separate signature.

The Consent Forms must be signed and dated by the patient or the patient's legally authorized representative before his or her participation in the study.

Due to the pandemic situation and restricted hospital access, the patient's legally authorized representative may consent remotely with appropriate documentation by the investigator or the authorized designee in accordance with applicable regulatory guidance. Where informed consent from the patient or the legally authorized representative is not feasible, exception from regulatory informed consent requirements may be permitted under certain circumstances in accordance with applicable law and IRB/EC policies.

The case history or clinical records for each patient shall document the informed consent process and that written informed consent was obtained prior to participation in the study.

The Consent Forms should be revised whenever there are changes to study procedures or when new information becomes available that may affect the willingness of the patient to participate. The final revised IRB/EC-approved Consent Forms must be provided to the Sponsor for health authority submission purposes.

If the Consent Forms are revised (through an amendment or an addendum) while a patient is participating in the study, the patient or a legally authorized representative must re-consent by signing the most current version of the Consent Forms or the addendum, in accordance with applicable laws and IRB/EC policy. For any updated or revised Consent Forms, the case history or clinical records for each patient shall document the informed consent process and that written informed consent was obtained using the updated/revised Consent Forms for continued participation in the study.

A copy of each signed Consent Form must be provided to the patient or the patient's legally authorized representative. All signed and dated Consent Forms must remain in each patient's study file or in the site file and must be available for verification by study monitors at any time.

MSTT1041A/UTTR1147A—Genentech, Inc.
88/Protocol GA42469, Version 4

For sites in the United States, each Consent Form may also include patient authorization to allow use and disclosure of personal health information in compliance with the U.S. Health Insurance Portability and Accountability Act (HIPAA) of 1996. If the site utilizes a separate Authorization Form for patient authorization for use and disclosure of personal health information under the HIPAA regulations, the review, approval, and other processes outlined above apply except that IRB review and approval may not be required per study site policies.

